### 7.3 HAUSER PATIENT DIARY

The Hauser Patient Diary will be used to collect information on how much time a participant spends in the different Parkinson's disease states:

- ON - Good or practically normal mobility
- ON with Troubling Dyskinesia – participant is troubled by involuntary twisting, turning movements. These movements are different from the rhythmic "tremor" which is a symptom of Parkinson's disease itself
- OFF - stiffness, marked decrease in mobility, and/or immobility
- ASLEEP - time spent sleeping.

The diary is divided into 30-minute sections starting at midnight and ending at 11:30 PM.

Participation in the study requires that participants demonstrate full understanding of the rating criteria and proficiency in completing the diary. At the Screening Visit, participants will be taught

how to use the diary by a member of the study site staff. At the end of the training session, participants and a site staff rater will concurrently but separately complete diary entries for 3 half hour periods. Diary concordance of at least 66% will be required for the participant to qualify for the study.

Participants are to complete this 24-hour diary of their Parkinson's disease symptoms twice per week (on 2 nonsequential days) for 3 consecutive weeks prior to the second screening visit (i.e., the Day -7 to Day -3 visit) (baseline entries), and on 2 nonsequential days during the week prior to Day 15, and Weeks 12 and 26.

The change from baseline in absolute number of daily hours in the “on without troublesome dyskinesias” state to the weeks prior to Day 15, Week 12 and Week 26 will be compared.

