## SCHEDULE OF ACTIVITIES

**Table 1: Schedule of Activities**

Study Day/Month	Screening		Surgery/ Hospital		UV	Day 15 ±2 days	Day 29 ±3 days	Week 12 ±7 days	Week 19 a ±7 days	Week 26/EW ±7 days
	Day -40 to Day -8	Day -7 to Day -3	Day 1	Day 2						
Informed consent	X b									
MRI of head c	X									X
 FDG-PET of head c	X									X
CT or MRI for presurgical planning	X d									
UK Parkinson's Disease Society Brain Bank criteria	X b									
Inclusion/exclusion criteria e	X b									
Demographics f	X b									
Medical/surgical history	X b									
Prior and concomitant medications g										►
AE assessment h										►
MDS-UPDRS Part 3 "off" state i	X b						X	X		X
MDS-UPDRS Part 3 "on" state repeated j	X b						X	X		X
Montreal Cognitive Assessment (MoCA)	X b							X		X
Beck Depression Inventory-II	X b							X		X
Physical examination	X b		X k		X					X
Vital sign measurements	X b		X l	X	X	X	X	X		X
Complete neurological examination	X b			X	X	X	X	X		X
12-lead ECG	X b				X	X				
Clinical laboratory evaluations (chemistry, hematology, coagulation, and urinalysis)	X b	X		X m	X	X m	X m	X m		X m
Serum pregnancy test (WOCBP only)	X b	X			X n					
Training and validation of Hauser Patient Diary o	X b									
Distribution of Hauser Patient Diary	X b			X			X	X		
Revised Hopkins Verbal Learning Test (HVLT-R)	X p									X
Trail Making Test (TMT)	X p									X
Stroop Color and Word Test (DKEFS version)	X p									X
Verbal fluency Test (DKEFS version)	X p									X

Study Day/Month	Screening		Surgery/ Hospital		UV	Day 15 ±2 days	Day 29 ±3 days	Week 12 ±7 days	Week 19 a ±7 days	Week 26/EW ±7 days
	Day -40 to Day -8	Day -7 to Day -3	Day 1	Day 2						
Digit Span	X p									X
MDS-UPDRS Part 1 (Non-Motor Experiences of Daily Living)	X p						X	X		X
MDS-UPDRS Part 2 (ADL)	X p						X	X		X
MDS-UPDRS Part 4 (Complications)	X p						X	X		X
Beck Anxiety Inventory	X p									X
Unified Dyskinesia Rating Scale	X p							X		X

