Parkinson's Disease Questionnaire-39 Scale	X p									X
Parkinson's Disease Sleep Scale-2	X p									X
Columbia-Suicide Severity Rating Scale	X p						X	X		X
EuroQol-5 Dimensions-5 Levels Survey	X p									X
Clinical Global Impression-Severity	X p									X
Clinical Global Impression-Improvement										X
Randomization	X q									
Surgery and related procedures			X							
Stereotactic imaging following frame placement (CT or MRI)			X							
Limited-cut CT at catheter tip to confirm localization following infusion (AAV-GAD groups only)			X							
Non-contrast CT of head within 24 hours after catheter removal (AAV-GAD groups only)				X						
Sham limited-cut CT at catheter tip to confirm localization following infusion (SHAM group only)			X							
Sham non-contrast CT of head within 24 hours after catheter removal (SHAM group only)				X						
Study drug administration			X							
Removal of catheter			X							
Removal of sutures and burr hole site assessment						X				
Anti-GAD and anti-AAV2 antibody evaluation (humoral immune response)		X					X	X		X

Study Day/Month	Screening		Surgery/ Hospital		UV	Day 15 ±2 days	Day 29 ±3 days	Week 12 ±7 days	Week 19 a ±7 days	Week 26/EW ±7 days
	Day -40 to Day -8	Day -7 to Day -3	Day 1	Day 2						
Hauser Patient Diary review		X				X r		X r		X r
Check on control of Parkinsonism, and other neurological events									X	

Note: If, despite all efforts to encourage the participant to continue in the study, the participant withdraws consent after Day 1, every effort should be made to complete the full panel of assessments scheduled for the Week 26 visit.

During visits that include the MDS-UPDRS assessment, the MDS-UPDRS Part 3 “off” state assessment should preferably be performed before any other assessments or questionnaires.

- a. Telephone visit. Participants will be contacted by telephone for assessment of AEs, changes in control of Parkinsonism, and other neurological events.
- b. Assessments preferably to be performed between Day -40 and Day -21.
- c. MRI and FDG-PET scans done for surgical screening will be used as baseline assessments. Due to the retention of the nylon/titanium cranial anchor base above the skull as a burr hole cover following removal of the infusion system, the specific MRI conditions detailed in the IFU must be taken into account for all post-surgical MRI scans.

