- d. If an MRI of the head is done at screening, the MRI for presurgical planning does not need to be done.
- e. The diagnosis of idiopathic PD will be made before any other screening procedure will take place.
- f. Demographics will include sex, age, race and ethnicity.
- g. Prior and concomitant medications will be recorded from date of informed consent form (ICF) signature till the final study visit on electronic case report form (eCRF). Changes in concomitant medications should be recorded before and after surgery.
- h. Participants will be contacted by telephone on Day 7 or 8 (6 or 7 days after study drug administration) for assessment of AEs.
- i. “Off” state scores will be obtained after at least 12 hours of holding dopaminergic medication.
- j. Participants may take additional levodopa (in addition to their usual dose) if needed to achieve the “on” state.
- k. Prior to the surgery
- l. Vital sign measurements: temperature, heart rate, respiratory rate, and blood pressure will be recorded before surgery, approximately every 30 minutes for at least the first 4 hours after start of infusion (this can be prolonged in 30-minute intervals if the infusion takes longer than 4 hours), and then at approximately 8 and 12 hours after the start of infusion. Of note, the participant may be transferred to an inpatient hospital service for the assessment of vital signs between 4 hours and 12 hours after start of infusion. Height will be measured at screening, whereas weight will be measured at both screening and Week 26 visits.
- m. Coagulation parameters will not be evaluated.
- n. Serum or urine pregnancy tests may be performed, as determined necessary by the Investigator or required by local regulation, to establish the absence of pregnancy at any time during the participation in the study.
- o. Inform the participant that the Hauser Patient Diary should be completed twice per week (on 2 non-sequential days) for 3 consecutive weeks prior to the second screening visit (i.e., the Day -7 to Day -3 visit). After baseline, the participant should complete the Hauser Patient Diary on 2 non-sequential days in the week prior to Day 15, and Week 12, and Week 26.
- p. Assessment only to be performed after the participant has qualified to enroll in the study.
- q. Randomization will occur after all inclusion and exclusion criteria have been met and surgery is scheduled.

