- r. Participants will be contacted by telephone approximately 1 week prior to their scheduled visits on Day 15, Week 12, and Week 26 to remind them to complete the Hauser Patient Diary on 2 non-sequential days during the week prior to their visit.

Abbreviations: AAV2 = adeno-associated virus serotype 2; ADL = activities of daily living; AE = adverse events; CT = computed tomography; DKEFS = Delis-Kaplan Executive Function System; ECG = electrocardiogram; EW = early withdrawal FDG = fluorodeoxyglucose; GAD = glutamic acid decarboxylase; HVLT-R = Revised Hopkins Verbal Learning Test; MoCA = Montreal Cognitive Assessment; MRI = magnetic resonance imaging; PD = Parkinson's disease; PET = positron emission tomography; TMT = Trail Making Test; UK = United Kingdom; UPDRS = Unified Parkinson's Disease Rating Scale; UV = unscheduled visit; WOCBP = women of childbearing potential.

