### 4.1 INCLUSION CRITERIA

1. Male or female
2. Age 25 to 85 years, inclusive.
3. Must sign an informed consent form (ICF) (or their legally acceptable representative must sign) indicating that he or she understands the purpose of, and procedures required for the study and is willing to participate in the study and consider participation in the long-term follow-up study.
4. Diagnosis of probable idiopathic Parkinson's disease by United Kingdom Parkinson's Disease Society Brain Bank criteria and no evidence of another Parkinsonian disorder.
5. Completed cranial MRI and FDG-PET during Screening. MRI and FDG-PET scans obtained during Screening will be used as baseline tests and will be reviewed to verify the diagnosis of Parkinson's disease.
6. Presence of typical features of Parkinson's disease and history of levodopa responsiveness demonstrated for at least 12 months prior to Screening.
7. Progressive Parkinsonian disability with demonstrated response from continued use of levodopa (or from other Parkinson's disease medications if part of the treatment regimen), but with insufficient response to medication (e.g., uncontrolled tremors, increased off-time, decreased on-time, motor fluctuations, dyskinesias, gait disturbance) or with intolerable side effects as judged by the Investigator.
8. Severe disability, which includes a practically defined "off" state MDS-UPDRS Part 3 (motor examination) score of  $\geq 25$  points after overnight omission of all Parkinson's disease medications.
9. Continued use of an unchanged stable anti-Parkinsonian drug regimen for  $\geq 4$  weeks prior to Screening.
10. Willingness to not add any new treatments for Parkinson's disease for the duration of the 6-month study period. Adjustments in the dose of dopaminergic medications are permitted when medically indicated.
11. Agrees not to participate in another interventional study until completion of this study and the long-term follow-up study.

12. Willingness to not receive DBS or any other approved or experimental surgical therapy for PD during the 6-month study period.
13. Receiving stable doses of other medications for any other underlying medical conditions for  $\geq 4$  weeks prior to Screening.
14. Must demonstrate a full understanding of the Hauser Patient Diary rating criteria and demonstrate proficiency in completing the diary by reaching at least 66% of diary concordance with a site rater.
15. A woman must be:

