### **6.2 STUDY PROCEDURES**

The Schedule of Activities (SoA) summarizes the frequency and timing of efficacy, safety, and immunogenicity assessments applicable to this study.

The diagnosis of idiopathic PD will be made before any other screening procedure takes place. During screening, assessments that are not part of the study entry criteria will be performed after the participant has qualified to enroll in the study (as per footnote “p” of the SoA [[Table 1](#)]).

All participants will be provided with an emergency card on enrollment to the study to enable 24-hour contact with study Investigators.

Participants randomly assigned to immediate treatment with AAV-GAD will be scheduled for surgery and complete the full battery of visits through the Week 26 visit (as described in the SoA), and then enter the long-term follow-up MGT-GAD-026 study.

Participants randomly assigned to sham surgery will follow the same visit schedule during the first 6 months, and then enroll in the long-term follow-up MGT-GAD-026 study, in which these participants will be offered treatment with AAV-GAD. The Week 26 visit of this study will serve as the Baseline visit of MGT-GAD-026.

Any medical condition already present at Screening should be recorded as medical history and not be reported as an AE unless the medical condition or signs or symptoms present at screening change in severity, frequency, or seriousness at any time during the study. In such a case, it should be reported as an AE.

The Week 19 visit is a telephone visit for assessment of AEs, changes in control of Parkinsonism, and other neurological events. The following actions must be taken if a participant fails to answer or return phone calls:

- The study-site personnel must attempt to contact the participant to reschedule the missed telephone visit as soon as possible.
- The Investigator or designee must make every reasonable effort to regain contact with the participant (where possible, 3 telephone calls, emails, fax).
- Should the participant continue to be unreachable, they will be considered to have missed the telephone visit.

During visits that include the UPDRS assessment, the MDS-UPDRS Part 3 “off” state assessment should preferably be performed before any other assessments or questionnaires. Site staff are to confirm that the last dose of dopaminergic medication(s) was taken by the participant at least 12 hours before performing the MDS-UPDRS Part 3 “off” state assessment (also see Section 7.2).

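### Diary days at Weeks 12 and 26 may fall on the evening of the medication hold for the 'off' exam, while a hold is less likely, and weighs less, in the baseline diary

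*Combined protocol and SAP*

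**What the plan says.** **Diary.** Section 7.3 describes a calendar-day record in 30-minute sections starting at midnight, with four states: ON, ON with troubling dyskinesia, OFF and asleep. Baseline entries are made on two non-adjacent days a week over the three weeks before the second screening visit (Day -7 to Day -3). Later entries are made "on 2 nonsequential days during the week prior to Day 15, and Weeks 12 and 26". Table 1, footnote r, ties those days to the participant's own visit: a telephone call about a week ahead is used "to remind them to complete the Hauser Patient Diary on 2 non-sequential days during the week prior to their visit". The endpoint is the change from baseline in daily hours ON without troublesome dyskinesia.

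**'Off' exam.** Footnote i of Table 1 says that 'off' "state scores will be obtained after at least 12 hours of holding dopaminergic medication". Section 6.2 has site staff confirm that the last dose was at least 12 hours earlier, and says that the 'off' "assessment should preferably be performed before any other assessments or questionnaires". Inclusion criterion 8 describes the exam as done "after overnight omission of all Parkinson's disease medications".

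**Status.** The Synopsis lists the diary among the exploratory activity assessments. Section 10.1.1 limits formal hypothesis testing to MDS-UPDRS Part 3 and GADRP. Section 10.1.4.1 compares mean change from baseline at Weeks 12 and 26 between the AAV-GAD groups and sham.

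**The concern.** The day before the Week 12 or Week 26 visit is an eligible diary day. If the exam is in the morning, the evening of that day lies within the hold, and the diary has no state for OFF time that the study itself has caused. Such time is scored like any other OFF time and comes out of the ON hours that the endpoint counts.

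The follow-up diary is more exposed than the baseline diary. A procedural loss could therefore be read as worsening since baseline, or as a decline since Day 15, when the diary is not followed by an 'off' exam. Only participants who happen to pick the day before the visit are affected. With groups of 5, 5 and 4, a few such choices can move a group mean.

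**Working it through.** The plan gives no sample size basis, SD or target difference for the diary, so there is no figure of its own to reproduce. The check compares schedule rows and then bounds the size.

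**1. Where diary and 'off' exam coincide (Table 1)**

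| Visit | Diary review | 'Off' exam |
|---|---|---|
| Screening, Day -40 to -8 | no | yes |
| Screening, Day -7 to -3 | yes | no |
| Day 15 | yes | no |
| Day 29 | no | yes |
| Week 12 | yes | yes |
| Week 26 | yes | yes |

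They coincide only at Weeks 12 and 26.

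**2. Whether a hold can enter the baseline diary**

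The three-week window runs from Day -28 to Day -8 if the second screening visit is on Day -7, and from Day -24 to Day -4 if it is on Day -3. The screening 'off' exam may be held from Day -40 to Day -8, preferably Day -40 to Day -21 (footnote b). The ranges overlap. The diary is taught at the Screening Visit, so a hold day at baseline needs screening to be split, with the exam after the training. That is possible but less likely than at follow-up.

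**3. Chance that the day before the visit is used**

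- Non-adjacent pairs in a 7-day week: C(7,2) - 6 = 21 - 6 = 15.
- Pairs that include the last day: 5 (partners are days 1 to 5).
- Share if all pairs are equally likely (an assumption): 5/15 = 33%.

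**4. Ceiling on the hours affected**

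Exam clock times are not in the documents, so those below are assumed. For a hold of L hours and an exam at clock hour h:

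- hold hours before midnight = max(0, L - h)
- ceiling in the two-day mean = those hours / 2
- average over random day pairs = ceiling × 5/15

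| Hold L | Exam | Before midnight | Ceiling, two-day mean | Average over random pairs |
|---|---|---|---|---|
| 12 h | 08:00 | 4 h | 2.0 h/day | 0.67 h/day |
| 12 h | 09:00 | 3 h | 1.5 h/day | 0.50 h/day |
| 12 h | 10:00 | 2 h | 1.0 h/day | 0.33 h/day |
| 12 h | 12:00 | 0 h | 0 | 0 |
| 14 h (assumed) | 08:00 | 6 h | 3.0 h/day | 1.0 h/day |

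**5. Weight at baseline against follow-up**

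Baseline has 2 × 3 = 6 diary days. Taking a simple mean, a 4-hour hold evening moves it by at most 4/6 = 0.67 h/day, against 4/2 = 2.0 h/day at follow-up. If both occurred, 2.0 - 0.67 = 1.33 h/day of the ceiling would remain in the change score.

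**The case against.** - **The hours are not all lost.** The hold is counted from the last dose. With the minimum hold and an 08:00 exam, that dose is at 20:00, so the four hours in question directly follow a dose. Section 7.2 expects the ON state about 2 hours after medication. What is lost is the effect of any later evening dose, and part of the evening is sleep, a separate diary state. This stands: the figures are ceilings, and the likely loss under the minimum hold is well below them. Longer holds, which the wording allows, could add more.
- **The hold is common to all arms.** A reader might infer a bias for or against AAV-GAD. The documents do not support that: allocation is randomized, raters and participants are blinded, and the hold rule is the same for everyone. What remains is a downward shift within each arm, plus chance imbalance in who is affected. The loss could differ by arm if treatment changes the unmedicated state, but nothing here establishes that for this trial.
- **The baseline may contain a hold too.** A reader might infer that baseline diaries are free of it. The schedule makes that likely but does not guarantee it.
- **Frequency.** Over two visits one could calculate 1 - (2/3)² = 56% of participants with at least one affected diary. That needs independent choices at Weeks 12 and 26. A participant who keeps the same diary days at both visits stays at 33%.
- **Exam first is a preference.** Exam times are open, and a noon exam with the minimum hold adds nothing.
- **A rule may exist elsewhere.** Analysis details are left to a SAP, and the supplied document contains no SAP text on diary days, so this cannot be checked.

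**Conclusion.** The point holds in limited form. As written, the plan lets study-imposed OFF time into the Week 12 and Week 26 diaries, with less exposure and less weight at baseline and none at Day 15. The consequences are a lower within-arm change in ON time and extra noise in small groups, not a built-in advantage for any arm.

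The size is unknown. It is bounded by the ceilings above, which rest on assumed exam times and on every hold hour before midnight being lost ON time. The 33% rests on random choice of diary days. Priority is low, because the endpoint is exploratory and descriptive in a trial whose primary objective is safety and tolerability. The change is still worth making because it costs almost nothing.

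**What to change.** In Section 7.3 and footnotes o and r of Table 1, add that both non-sequential diary days must be completed before the calendar day on which the hold for the 'off' exam starts. Agree the two dates in the existing reminder call. Apply the same rule to baseline diary days whenever the screening 'off' exam falls within the three-week window.

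The hold, the exam and the visit schedule are untouched. With the hold starting the evening before the visit, the hold then contributes 0 hours to the diary. The cost is one sentence, two footnotes and one fewer eligible day per week: six days still allow C(6,2) - 5 = 15 - 5 = 10 non-adjacent pairs.

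Prevention is simpler than correction in the analysis. Setting aside entries made during the hold would need its start time, and no section explicitly requires that to be recorded; Section 6.2 asks staff only to confirm that 12 hours have passed.

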## 8 SAFETY ASSESSMENTS

Safety will be evaluated by vital signs, neurological examinations, physical examinations, ECGs, radiographic imaging (CT and MRI), clinical laboratory evaluations, descriptive analysis of AEs (including incidence, severity, seriousness, and relatedness), immune response, and the Columbia-Suicide Severity Rating Scale over the 6-month duration of the study. Safety will continue to be assessed within the proposed separate long-term follow-up study, assuming regulatory approval.

### 8.1 DATA AND SAFETY MONITORING BOARD

A DSMB will be established to ensure the continuing safety of the participants enrolled in this study. This committee will consist of neurosurgeons and neurologists with expertise in the assessment and treatment of participants with Parkinson's disease and with backgrounds in clinical research. The committee will meet at predefined timepoints, or on an ad hoc basis at the request of the sponsor to provide expert consultation on specific issues as described in the DSMB charter.

### 8.2 ADVERSE EVENTS

Adverse event definitions are provided in [Table 2](#).

**Table 2: Adverse Event Definitions**

Adverse Event (AE)	Any untoward medical occurrence in a clinical study participant administered a medicinal product and which does not necessarily have a causal relationship with this product.
Adverse Drug Reaction (ADR)/Adverse Reaction (AR)	Any untoward and unintended response to an investigational medicinal product related to any dose administered.
Serious Adverse Event (SAE) or Serious Adverse Reaction (SAR)	Any AE or AR that at any dose: 

• Results in death

• Is life threateninga

• Requires hospitalization or prolongs existing hospitalizationb

• Results in persistent or significant disability or incapacity

• Is a congenital anomaly or birth defect

• Or is another important medical conditionc

Unexpected Serious Adverse Drug Reaction	A SAR whose nature, severity or outcome is not consistent with the reference safety information (RSI). As AAV-GAD is an investigational medicinal product, the RSI is included in the IB for this study.

a: Life threatening refers to an event in which the participant is at risk of death at the time of the event; it does not refer to an event that might hypothetically cause death if it was more severe (e.g., a silent myocardial infarction).

b: Hospitalization is defined as an inpatient admission, regardless of length of stay. Hospitalization for an elective procedure for a pre-existing condition does not constitute an SAE.

c: Medical judgment should be exercised in deciding whether an AE or ADR is serious in other situations. Important AEs or ARs that may not be immediately life threatening or result in death or hospitalization but may seriously jeopardize the participant by requiring intervention to prevent one of the other outcomes listed in the table (e.g., a secondary malignancy, an allergic bronchospasm requiring intensive emergency treatment, seizures or blood dyscrasias that do not require hospitalization, or development of drug dependency).

Adverse events include:

- An exacerbation of a pre-existing illness
- An increase in the frequency or intensity of a pre-existing episodic event or condition
- A condition (regardless of whether PRESENT prior to the start of the study) that is DETECTED after study drug administration (or sham surgery). (This does not include pre-existing conditions recorded as such at screening.)
- Continuous persistent disease or a symptom present at baseline that worsens following administration of study drug (or sham surgery)
- Overdose of study drug

Adverse events do NOT include:

- Medical or surgical procedures: the condition that leads to the procedure is an AE
- Pre-existing disease or a condition present before treatment that does not worsen
- Hospitalization where no untoward or unintended response has occurred, e.g., elective cosmetic surgery

